9.2 Sample Size and Randomization

Based on similar viral infectivity studies evaluating antiviral mouth rinse efficacy, we were able to run power calculations to estimate effect size and determine sample size as a function of length of mouth rinse time course. The sample size is justified by a paired t-test on outcomes between time points. With simultaneous comparisons, the sample size n=43 for each mouth rinse can detect the effect size in Cohen's $d = 0.8$ at 30 minutes, which is between medium and large, under 80% power and 0.016 type-I error rate by Bonferroni correction.¹² To account for 14% of patients having no virus in their saliva and 10% of patients producing insufficient saliva, we plan to enroll 55 participants per arm.

The statistical consultant on this project will create a block randomization tool for the study staff; the unblinded staff member will randomize a participant once enrollment compliance has been confirmed and consent has been given. The participant's group assignment will then be communicated to the blinded study staff. IRB approved study personnel will ask participants screening questions to confirm eligibility for enrollment. After consent and screening, the randomization tool will be used by study staff to assign the subject to a study group.

The researcher responsible for collecting the salivary samples will be blinded to the mouthwash solution, as they will be given a pre-aliquoted mouth rinse in an unlabeled tube to provide to the patient for the rinse.

The PI, Co-I, study coordinators and study personnel who work for GoHealth are authorized to break the blinding based on emergency medical necessity such as if a patient suffers an allergic or adverse reaction to one of the mouth rinses. Though highly unlikely as all mouth rinses are sold commercially at Walgreens and CVS, adverse or allergic reactions are possible. Using the numerical code associated with the participant and mouth rinse syringe, the study personnel responding to the emergency can reference the block randomization schedule to determine the mouth rinse type, to inform the emergency medical workers, poison control or the emergency room what type of mouth rinse product led to the reaction.

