2.2 Study Rationale

One promising strategy to reduce clinical spread is use of antiviral mouth rinses to inactivate SARS-CoV-2 infectability in saliva. Several commercially available mouth rinses have promising *in vitro* data with SARS-CoV-2 and *in vivo* data with other enveloped viruses, with a proposed mechanism of membrane disruption.^{3,11} Ethanol solutions (21% EtOH) have been shown to reduce SARS-CoV-2 viral infectivity levels *in vitro*, and in patients suffering Herpes Simplex Virus-1 flare-ups, a 30 second oral rinse significantly reduced salivary infectivity for over 30 minutes.¹² Cetylpyridinium chloride has promising *in vitro* data for inactivating SARS-CoV-2 infectivity.¹³ Minimal *in vivo* clinical data regarding SARS-CoV-2 exists to-date for most oral rinses.

Despite promising *in vitro* data, there is a dearth of *in vivo* clinical trials interrogating the efficacy of mouth rinses on reducing salivary SARS-CoV-2 viral infectivity. Given the rapid transmission and widespread distribution of the COVID-19 pandemic and its new variants, the development of protocols and treatments mitigating transmission represent a major and urgent unmet public health need; this study will rigorously address the *in vivo* utility of widely available oral rinses in limiting SARS-CoV-2 viral infectivity and their acceptability in the dental healthcare setting.⁵⁻⁸

Like other enveloped viruses, coronaviruses are surrounded by a lipid bilayer which allows for spike glycoproteins required for infection to be inserted.³ The mouth rinses proposed

in this study have shown success in previous studies in disrupting this lipid envelope in other viruses, and there is promise that they will do the same to the SARS-CoV-2 virus. Effect size: Based on our similar viral load studies evaluating mouth rinse efficacy against SARS-CoV-2 and studies about other enveloped viruses, we used power calculations to estimate effect size and determine sample size as a function of length of mouth rinse time course. With simultaneous comparisons across time points (T0-T1, T1-T2, T0-T2, T2-T3, T0-T3, T1-T3), the sample size $n=43$ for each mouth rinse can detect the effect size in Cohen's $d = 0.8$ at 30 minutes, which is between medium and large, under 80% power and 0.016 type-I error rate by Bonferroni correction.¹² To account for 14% of patients having no virus in their saliva and 10% of patient producing insufficient saliva, we plan to enroll 55 participants per arm.

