3. STUDY DESIGN

One of the aims of this placebo-controlled, randomized, double-blinded study is to determine the efficacy of antiseptic mouthwashes on reducing SARS-CoV-2 cellular infectivity in COVID+ patient saliva (described above). Asymptomatic and symptomatic SARS-CoV-2+ subjects will be enrolled in the study (according to Inclusion and Exclusion Criteria - Section A.3). Symptomatic SARS-CoV-2+ subjects will be enrolled within 10 days of symptom onset and/or within 10 days of initial positive test; asymptomatic SARS-CoV-2+ subjects will be enrolled within 10 days of initial positive test. Positive test results will be accepted if they are provided by a medical professional or official testing site. Results can appear either in the UNC electronic medical record or be printed from an established testing site such as UNC, a local pharmacy, a medical practice, or an established lab. At-home positive test results will be accepted when they are confirmed by study

personnel with a rapid antigen test at the time of visit. Subjects will be seen and samples collected in the isolated Clinical Research Space associated with the GoHealth Clinic (Adams School of Dentistry, UNC Chapel Hill, North Carolina, USA). SARS-CoV-2+ subjects will be enrolled within 10 days positive test. Study participants who meet all inclusion criteria without any exclusion criteria will be randomized to either an experimental or control group using a block randomization tool.

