Participants will be asked to give a baseline salivary sample (5ml over 5 minutes) and then asked to rinse with an unlabeled (blinded) antiseptic mouth rinse for 60 seconds according to the table below. The rinses and control will be similar in appearance visually, such that a double-blind can be maintained. The research assistant ([name]) will be the sole unblinded staff member who will perform randomization and communicate the subject's group assignment to blinded study staff, in advance of the visit based on the block randomization schedule. The unblinded staff member will set-up the rinses for the participants appointment minimizing the possibility of study staff being able to identify the blinded rinses. In the instance that [name] is unavailable, [name] or [name] will perform randomization and set-up the rinses. Blind will be strictly maintained except in the case of medical emergency requiring reveal of an individual's rinse identity. The product group key will be provided to the analyzing statistician at the conclusion of the clinical study.

mouth rinse*	Number of participants (sample size)	Group
26.9% ethanol plus essential oils	84	Experimental
0.1% Cetylpyridinium Chloride	84	Experimental
Sterile water	84	Control

**All mouth rinses are commercially available in the USA, routinely used in clinical settings, and will be used in an on-label manner.*

After the participant expectorates the mouth rinse, research staff will collect another salivary sample (T_0 , 2 mL over 5 minutes). During a 10 minute recuperation period, the study participants will answer demographics survey questions and questions regarding the taste, color, flavor and general acceptability of using the mouth rinse as part of routine dental and medical visits as well as in social settings. At 15 minutes post-rinse, the participant will be asked to provide an additional saliva sample (2 mL over 5 minutes), followed by another 10 minute recuperation period. This sequence will be repeated for at

the 30, 45 and 60-minute time points post rinse. At 60 minutes, the study participant will give their final salivary sample (2 mL over 5 min), and study participation will conclude.

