All salivary samples will be collected on ice in sterile 15 mL conical vials labelled “COVID Core” and using pre-printed labels including patient’s random alphanumeric study ID. Saliva samples will be cataloged and stored at the UNC Delta COVID Translational Initiative (also known as the Covid-19 Core) for future qRT-PCR and viral infectivity assays. Samples will be transported on ice from the collection site to 4403A Koury Hall in leak proof biohazard bags. Samples will be processed according to the **sample processing and outcomes** procedure (below).

Following study participation completion, participants will receive \$50 compensation in the form of a Visa gift card.

During the period that the COVID+ study participants are present in the clinic and giving saliva samples, we will inquire about their comfort. If participants exhibit signs of distress, research study staff will contact emergency medical responders (present in the building) to visit the patient and if deemed appropriate, the participants will be escorted to UNC hospital (adjacent building).

This time course analysis design will allow us to determine if any of the antiseptic mouthwashes are effective at reducing SARS-CoV-2 in salivary secretions of COVID-19+ study participants as well as to determine the therapeutic window if effective. We have designed this study to recapitulate a standard oral exam and procedure time (~1 hr in length). Further, the design will allow for a kinetic analysis of viral shedding in salivary secretions and to determine the most effective mouth rinse.

Sample processing and outcomes

Sample processing: Following collection, saliva samples will be processed according to existing BSL2+ SOP protocols (COVID Core, UNC (PI: [name] and [name]) by pre-authorized personnel. Samples will be assessed for **1**) molecular presence of SARS-CoV-2, **2**) salivary antibody and cytokine responses to SARS-CoV-2 and **3**) in vitro infectibility. All samples have labels with only alphanumeric identifiers thus maintaining the blind and protecting PHI through the entire laboratory analysis process.

1. Molecular analysis: For molecular analysis, samples will be inactivated by adding 2 mL of extraction buffer to each 500 uL saliva aliquot (4:1 ratio) and mixed by inversion. These samples will be further aliquoted at 250uL in 1.5 mL Eppendorf tubes and stored in an “Inactivated Samples -80 °C Freezer” until further analysis.

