9. STATISTICAL CONSIDERATIONS

9.1 General Design Issues

A double-blinded, randomized controlled trial was chosen as the study design. It allows us to collect human based data on the effects of commercially available mouth rinses on salivary infectivity and viral load. A crossover study was not pursued because the repeated use of different mouth rinses is likely to confound the results. A 1-hour time-course was chosen to correspond with the average length of most dental procedures. Fifteen minute intervals were chosen to evaluate viral kinetics over time, and to see when infectivity rebounds post- mouth rinse.

Statistical Hypothesis

The central hypothesis of this study is that a 60 second antiseptic mouth rinse will effectively reduce viral infectivity (>50%) of SARS-CoV-2 for a minimum of 30 minutes duration.

The secondary hypothesis is that a 60 second mouth rinse will be well tolerated in a clinical care setting by a majority of patients and providers.

Sample Size Considerations

Based on our similar viral load studies evaluating mouth rinse efficacy against SARS-CoV-2 and other enveloped viruses, we used power calculations to estimate effect size and determine sample size as a function of length of mouth rinse time course.¹² With simultaneous comparisons, the sample size n=43 for each mouth rinse can detect the effect size in Cohen's $d = 0.8$, which is between medium and large, under 80% power and 0.016 type-I error rate by Bonferroni correction.¹² To account for 14% of patients having no virus in their saliva and 10% of patients producing insufficient saliva, we plan to enroll 55 participants per arm.

Statistical analysis of our deidentified data will be performed by [name], the statistician on this project.

Primary Outcomes

The analyses will compare viral RNA level (qRT-PCR) and viral infectivity levels between mouth rinse types and across the time course

Data generated from the qRT-PCR assays will be presented as mean standard deviation for normally distributed data and as median [Interquartile range] for non-normally distributed data. P values will be reported as two tailed. Between group comparisons will be performed using a Student's t test or Mann-Whitney U test. Normality will be assessed using the Kolmogorov-Smirnov test, and logistic regression will be performed with robust standard errors.

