Power Calculation: Based on our similar viral load studies evaluating mouth rinse efficacy against SARS-COV-2 and other enveloped viruses, we used power calculations to estimate effect size and determine sample size as a function of length of mouth rinse time course.¹² The sample size is justified by a paired t-test on outcomes between time points. With simultaneous comparisons, the sample size n=43 for each mouth rinse can detect the effect size in Cohen's d =0.8, which is between medium and large, under 80% power and 0.016 type-I error rate by Bonferroni correction.¹² To account for 14% of patients having no virus in their saliva, we plan to enroll 55 participants per arm. Analyses will compare viral RNA level (qRT-PCR) and viral infectivity levels between mouth rinse types and across the time course. ANCOVA models will be utilized to look at changes in viral load and infectivity logarithmically before and after treatment.

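### The stated 80% power at n=43 does not follow from the paired t-test named, and no detectable rinse-versus-water difference is given

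*Combined protocol and SAP*

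**What the plan says.** The power statement appears four times: Section 2.2, Section 9.1 (Sample Size Considerations), Section 9.2 and Section 9.5 (Power Calculation). Sections 9.2 and 9.5 name the test: "The sample size is justified by a paired t-test on outcomes between time points". Section 9.5 continues that "the sample size n=43 for each mouth rinse can detect the effect size in Cohen's d =0.8, which is between medium and large", and Section 9.2 closes the statement "under 80% power and 0.016 type-I error rate by Bonferroni correction". Sections 2.2 and 9.1 repeat the figures without naming a test.

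Section 2.2 alone lists the comparisons: "With simultaneous comparisons across time points (T0-T1, T1-T2, T0-T2, T2-T3, T0-T3, T1-T3". It does not define T0 to T3, and it ties the effect to 30 minutes. Section 3 uses one of these labels: "After the participant expectorates the mouth rinse, research staff will collect another salivary sample (T_0".

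These four sections plan 55 per arm. The Précis and the table in Section 3 give 84 per arm in three arms, one of them sterile water.

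Section 3 describes the trial thus: "One of the aims of this placebo-controlled, randomized, double-blinded study is to determine the efficacy of antiseptic mouthwashes", and expects the design "to determine the most effective mouth rinse". Section 9.1 states: "The analyses will compare viral RNA level (qRT-PCR) and viral infectivity levels between mouth rinse types and across the time course". Section 9.5 repeats this and adds an ANCOVA on the log scale, without saying that it compares arms or which covariate it uses.

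**The concern.** A power statement should be reproducible from its own inputs. Here the test, d, alpha and power are all given, yet together they do not lead to 43. The standardiser of d is missing, as are the familywise alpha, the number of comparisons it is divided by, and whether 80% applies to each comparison or to several jointly.

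The calculation also concerns only change over time within one arm. A fall in titre after rinsing could partly reflect dilution or repeated expectoration, and the water arm is what separates that from an antiviral effect. The randomised contrast therefore carries the efficacy conclusion, but the reader is not told what difference it can detect. Nor can the reader work it out from the plan, because the number of evaluable participants depends on whether 55 or 84 are enrolled.

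**Working it through.** **Inputs.** n=43, d=0.8, alpha 0.016, 80% power, paired t-test (Sections 9.2 and 9.5). Losses of 14% (no virus) and 10% (insufficient saliva) (Sections 2.2, 9.1 and 9.2). A two-sided test is assumed: Section 9.1 reports two-tailed P values, but the power statement is silent. All power figures use the noncentral t distribution.

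**1. The plan's own figure, d on the SD of differences.** Noncentrality = d × √n = 0.8 × √43 = 5.25, against a critical t (42 df) of 2.51.
- Power at n=43 is 99.6%.
- Power is 78.6% at n=19 and 81.4% at n=20, so 80% needs 20. A one-sided test needs 17.
- Detectable d at n=43 with 80% power is 0.51.

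The stated 80% at n=43 is not reproduced.

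**2. d on the raw SD.** The paired effect is 0.8 / √(2(1−ρ)), where ρ is the correlation between time points.
- ρ=0: effect 0.566, power 88%.
- ρ=0.25: effect 0.653, power 96%.
- ρ=0.5: effect 0.800, power 99.6%.
- Power falls to 80% only at ρ of about −0.21.

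**3. Two-sample reading.** Noncentrality = 0.8 × √(43/2) = 3.71. Power at alpha 0.016 is 89%, and 35 per arm gives 80%.

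**4. What would give about 80% at n=43.** Each of these needs an input the documents do not state:
- two-sample at alpha 0.05/9: 80.3%;
- paired, raw-SD d, ρ=0, alpha 0.05/6: 82.0%;
- paired at 0.016 with ρ of about −0.21: 80%;
- joint power at 0.016 with raw-SD d=0.8 at every post-rinse time, by simulation: about 80% for two contrasts with the first sample at correlation 0, and about 81% for three at correlation 0.1.

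**5. Loss step.** 43 / 0.86 / 0.90 = 55.6, close to the planned 55. The unexplained figure is therefore the 43. No section derives 84.

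**6. Alpha.** If the familywise level is 0.05 (not stated), 0.05/3 = 0.0167 and 0.05/6 = 0.0083. The stated 0.016 fits three comparisons, while Section 2.2 lists six.

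**7. Rinse versus water.** Evaluable per arm: 55 × 0.86 × 0.90 = 42.6, about 43; 84 × 0.86 × 0.90 = 65.0. For an unadjusted two-sample t-test on post-rinse values with 80% power at alpha 0.016, the detectable d is:
- 43 per arm: 0.71;
- 65 per arm: 0.58.

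If low-saliva participants are replaced over and above the enrolled number, these become 55 × 0.86 = 47 per arm (0.68) and 84 × 0.86 = 72 per arm (0.55).

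Baseline-adjusted ANCOVA multiplies d by about √(1−r²), where r is the correlation with the pre-rinse value. For an assumed r of 0.3 to 0.7 (the documents give none), 0.71 becomes 0.68 to 0.51, and 0.58 becomes 0.55 to 0.41. Unadjusted change scores multiply d by √(2(1−r)): at r=0.3, 0.71 × √1.4 = 0.84, which is larger than the unadjusted value.

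**8. Targets on the log scale.** A 50% reduction (Section 9.1) is log10(2) = 0.30 log10. A 95% reduction (Sections 1.1 and 9.4.1) is log10(20) = 1.30 log10. Neither is stated as a difference from water, and no SD is given that would link them to d.

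**The case against.** The best defence is that the statement is under-specified rather than wrong. Every version speaks of simultaneous comparisons, so the 80% may be joint power, and step 4 shows that joint power at near-zero correlation can reach it. The inputs are said to come from the sponsor's earlier studies, which the reader cannot see. This has force: the documents do not show which element is off, and no particular alternative calculation can be attributed to the sponsor. It does not rescue the text, because neither joint power nor a correlation is stated.

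Several stronger readings are tempting but unsupported:
- **The trial is underpowered.** The error runs the other way: 43 exceeds what the named test needs, and a two-sample reading still has 89% power at d=0.8.
- **Alpha 0.016 contradicts the six pairs.** That holds only for a familywise 0.05. Six comparisons at 0.10 would also give 0.0167.
- **None of the six pairs includes the pre-rinse sample.** That follows only if Section 3's label is carried into Section 2.2. T0 as pre-rinse and T3 as 30 minutes is the natural reading, since Sections 6.2.5 and 8 require exactly the baseline, immediate, 15- and 30-minute samples. The labels simply need aligning.
- **Deducting low-saliva participants conflicts with replacing them.** It need not, if the 55 counts those who are removed and replacement is how 43 evaluable is reached.

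**Conclusion.** The point holds in two parts. First, the stated 80% is not reproduced: the test named gives 99.6% at n=43 with d on the SD of differences, and 88% or more per comparison with d on the raw SD and non-negative correlation. This assumes a two-sided test and per-comparison power. The basis of the 43 is unknown, and the mismatch is conservative.

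Second, no detectable rinse-versus-water difference is stated although that comparison is planned and randomised. Under the plan's own losses and alpha 0.016 it would be d=0.71 if 55 per arm are enrolled and d=0.58 if 84 are. These values are upper bounds only for an ANCOVA adjusted for pre-rinse log10 titre. They are not bounds for change scores or for a Mann-Whitney test, both of which the plan could use. The contradiction between 55 and 84 is plain and determines which value applies. This should be fixed, but it does not by itself put the design in doubt.

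**What to change.** 1. In Sections 2.2, 9.1, 9.2 and 9.5, give one consistent set: test, standardiser of d, familywise alpha, number of comparisons, per-comparison or joint power, and time-point labels that match Section 3. If the per-comparison paired test at 0.016 with d on the SD of differences stands, state 99.6% power at d=0.8, or d=0.51 at 80% power.
2. Reconcile 55 with 84 per arm, and say whether the enrolled number counts low-saliva participants who are replaced.
3. State the detectable rinse-versus-water difference at the resulting evaluable number, as d and in log10 units using the SD from the sponsor's earlier study, next to the >50% and >95% targets.
4. Specify that the ANCOVA in Section 9.5, adjusted for pre-rinse log10 titre, is the between-rinse analysis and compares each active rinse with water. Keep the within-patient analysis.

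The cost is text in four sections, one enrolment number made consistent and one short recalculation. Pre-rinse saliva and the water arm are already in the design, so no new samples are needed. The downside is that a between-arm detectable difference must be stated openly. It is on a different scale from the paired d (raw SD rather than SD of differences; the two coincide only at correlation 0.5), so the text should warn against comparing them directly.

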1. STUDY OBJECTIVES

1.1 Primary Objective

The primary objective of this study is to determine the efficacy of antiseptic mouthwashes on reducing SARS-CoV-2 cellular infectivity in COVID+ patient saliva. *We hypothesize that COVID-19+ patients will have a >95% reduction in SARS-CoV-2 viral infectivity following a 60 second oral rinse with an antiseptic mouth rinse and that this reduction will persist for at least 30 minutes.* This primary objective will focus on quantifying SARS-CoV-2 viral infectivity and RNA level using an *in vitro* infectivity assay and quantitative real time PCR. This objective provides urgently needed data to guide healthcare workers on the proper use of specific commercially available mouthwashes capable of reducing SARS-CoV-2 viral infectivity and potentially limiting COVID-19+ transmission.

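### The persistence hypothesis must hold at every sample through 30 minutes, but the plan splits alpha over time points, quotes single-comparison power, and gives no success rule or joint power

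*Combined protocol and SAP*

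**What the plan says.** Section 1.1 hypothesises a reduction in infectivity of more than 95% after the rinse and "that this reduction will persist for at least 30 minutes"; section 9.4.1 repeats this. The Statistical Hypothesis in section 9.1 has the same form with a different threshold: the rinse will "effectively reduce viral infectivity (>50%) of SARS-CoV-2 for a minimum of 30 minutes duration". Section 3 places post-rinse samples at 0, 15, 30, 45 and 60 minutes, and says the time course serves to find out which rinses work "as well as to determine the therapeutic window if effective".

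The sample size is built differently. Section 2.2 refers to "simultaneous comparisons across time points (T0-T1, T1-T2, T0-T2, T2-T3, T0-T3, T1-T3"), and section 9.2 justifies n = 43 per rinse by a paired t-test between time points, for Cohen's d = 0.8 at 30 minutes, "under 80% power and 0.016 type-I error rate by Bonferroni correction". Sections 9.1 and 9.5 repeat the figures.

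No section says which times must succeed for the hypothesis to be accepted, gives a joint power, or states how the length of the window will be decided.

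**The concern.** A claim that an effect lasts through 30 minutes fails if the effect is absent at any of the three samples in that period. The multiplicity correction and the power statement should match that form, and they do not. Bonferroni protects against a false claim at any one of several times. The hypothesis needs a true effect at all of them.

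Three things follow. The correction is stricter than the claim requires. The quoted power belongs to one comparison, not to the claim. And without a rule over times, a rinse that succeeds at 30 minutes but not at 15, or only at the immediate sample, has no defined interpretation. The therapeutic window has no confirmatory definition either.

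**Working it through.** **1. Is a split over times needed?** The null for the persistence claim is that there is no reduction at one or more of 0, 15 and 30 minutes. If it is true, at least one time has no effect. The chance that all three tests reject cannot exceed the chance that the test at that time rejects, which is at most alpha. Each test can therefore run at the full alpha allotted to the claim (the intersection-union principle). What remains is multiplicity across the two active rinses: 0.05/2 = 0.025 each if split equally.

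**2. The plan's own figure.** Inputs from sections 9.1 and 9.2: n = 43, d = 0.8, alpha 0.016, two-sided. Power is the probability that a noncentral t exceeds its critical value in either direction.

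- Paired t-test, as stated: noncentrality 0.8 × √43 = 5.25, 42 df. Power 99.6%; n = 20 gives 80%.
- Two-sample t-test against water: noncentrality 0.8 × √(43/2) = 3.71, 84 df. Power 89.2%; n = 35 per arm gives 80%.

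Neither reproduces 80% at n = 43. The alpha is also unclear: 0.05/3 = 0.0167, whereas the six listed pairs would give 0.05/6 = 0.0083.

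**3. Joint power at n = 43.** Assume d = 0.8 at each of 0, 15 and 30 minutes and a common correlation r between the test statistics; the documents give none. With single-test power p, joint power is the trivariate normal probability that all three components fall below z(p).

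| Test | Alpha | Single | Joint, r = 0 | r = 0.5 | r = 0.9 |
|---|---|---|---|---|---|
| Paired | 0.016 | 99.6% | 98.8% | 98.9% | 99.3% |
| Paired | 0.025 | 99.8% | 99.3% | 99.4% | 99.6% |
| Two-sample | 0.016 | 89.2% | 70.9% | 76.6% | 83.9% |
| Two-sample | 0.025 | 92.1% | 78.1% | 82.2% | 87.9% |

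**4. Taking the quoted 80% at face value.** The noncentrality is z(0.992) + z(0.80) = 2.409 + 0.842 = 3.25. At 0.025 the same data give Φ(3.25 − 2.241) = 84% per test.

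| Alpha | Single | Joint, r = 0.5 | r = 0.7 | r = 0.9 |
|---|---|---|---|---|
| 0.016 | 80% | 61% | 66% | 72% |
| 0.025 | 84% | 68% | 72% | 78% |

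If the effect wanes, with the immediate and 15-minute effects assumed 1.5 and 1.25 times the 30-minute effect, joint power at 0.016 is 78–80% for r = 0.5 to 0.9.

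**5. Cost of the stricter level.** For one test at 80% power, the sample-size ratio of 0.016 to 0.025 is ((2.409 + 0.842)/(2.241 + 0.842))² = 1.11, or about 11%.

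**The case against.** The strongest reply is that the Bonferroni family may not be the persistence tests at all. Section 2.2 lists all six pairs among T0 to T3, including later-time pairs that describe kinetics. Section 3 attaches the T0 label to the point after expectoration where "research staff will collect another salivary sample", and on that labelling none of the six pairs involves the pre-rinse baseline. Locating the rebound, an aim in section 9.1, is not an all-must-succeed claim, and error control there is legitimate. This stands: the correction is unnecessary only for the persistence hypothesis. It also means that the plan does not say which comparisons decide that hypothesis.

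Second, Bonferroni is valid and conservative, so there is no type I error problem. That also stands.

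Third, a reader might infer from the 61–72% figures that the trial is underpowered for its hypothesis. The documents do not support this. Those figures require 80% to be the true single-test power, and the stated paired test gives 99.6%. They also require equal effects at all three times; if the effect is weakest at 30 minutes, which fits the rebound aim, joint power is close to the quoted 80%. The précis and section 3 give 84 per arm rather than the 55 in section 9.2. After losses of 14% and 10%, 84 leaves about 64 (84 × 0.76 = 63.8), and two-sample joint power at 0.016 is then 94–97%.

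Fourth, a reader might put the penalty at 35% by comparing 0.016 with 0.05, since ((2.409 + 0.842)/(1.960 + 0.842))² = 1.35. With two active rinses still sharing alpha, the relevant comparison is with 0.025, and the penalty is about 11%.

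**Conclusion.** The mismatch is real but moderate. As worded, the hypothesis is an all-times claim through 30 minutes. It needs no alpha split over times, and the quoted 80% was not calculated as its joint power. With n = 43 and d = 0.8 at each time, moving from 0.016 to 0.025 makes almost no difference for the paired test (about 99% either way) and raises joint power from 71–84% to 78–88% for a between-arm test. These ranges rest on equal effects at the three times and an assumed correlation of 0 to 0.9.

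A power shortfall is not shown, and the correction is not misplaced for every aim. The main loss is interpretive: there is no stated success rule over time and no rule for the therapeutic window. The change is worth making because it removes an unneeded penalty and supplies both rules.

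**What to change.** For the persistence claim, replace Bonferroni over time with a fixed sequence within each active rinse: immediate, 15, 30, 45, then 60 minutes. Compare each with the pre-rinse baseline or with water, whichever the primary analysis specifies. Run each test at that rinse's alpha (0.025 if 0.05 is split equally over the two active rinses), require the difference to be in the direction of reduction, and stop at the first failure. The hypothesis is met if the sequence passes 30 minutes; the window is the last time passed.

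Give the remaining pairwise time comparisons their own error control or label them exploratory, and define T0 to T3. Restate power as joint power through 30 minutes, with the effect assumed at each time and the assumed correlation. In the same edit, reconcile 43, 80% and 0.016 with the named test, 55 with 84 per arm, and the 95% with the 50% threshold. A test against no change shows a reduction, not one of either size.

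The cost is SAP wording; no new data are needed. The downside is that failure at an early sample blocks confirmatory claims at later ones, which is consistent with a hypothesis of continuous effect from the rinse onward.
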